- ii. **Exercise:** Sedentary lifestyle is associated with increased morbidity and mortality³³ and exercise training has been demonstrated to improve a number of important risk factors of medical burden (i.e., weight, cholesterol, insulin level^{34, 35}). Exercise may be dually beneficial for BD given that it has also been found to improve mood^{36, 37}. In a unipolar depressed sample, exercising 3 days/week for 45-min was as effective in reducing depressive symptoms as an antidepressant (i.e., sertraline)^{38, 39}, with promising data for bipolar samples⁴⁰. Given the duality of exercise benefit for mental health, interventions are needed to increase lifestyle activity.
- iii. **Wellness:** Individuals with BD make poor food choices³¹ and use maladaptive coping strategies for stress, such as smoking, that increase their medical burden. For example, smoking in BD populations has been shown to increase heart disease mortality⁴¹. Individuals with BD have dysregulated behavioral activation systems⁴² which may explain why they chose rewarding activities (i.e., cigarettes, caffeine), opposed to healthier coping skills. It is essential that an intervention reinforce the importance of making healthy lifestyle choices (i.e., food choices, lifestyle activity, reducing caffeine).

II. SPECIFIC AIMS

The purpose of this research is to develop and test the feasibility and acceptance of a theoretically integrated treatment to address the impact of medical comorbidity of individuals with BD, while exploring its efficacy, whether it improves overall functioning and symptoms, as well as examine a potential moderator and mediator of treatment response. NEW Tx is a proposed solution to this problem as it builds upon previous empirical studies in healthy populations as well as the limited literature on lifestyle modification with serious mental illness. NEW Tx also integrates and modifies treatment strategies, such that it can be administered by a sole provider who is skilled in intervention and assessment of medical comorbidity and BD. NEW Tx is not intended to replace the need to collaborate with other providers, and strongly encourages such support as needed, but is a first-line, adjunct treatment to reduce the medical burden in individuals with BD.

A. Primary Aims

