- i. **Aim 1:** Feasibility and Acceptance of NEW Tx in the Nonrandomized Trial (N=6). *Hypothesis 1a:* A preliminary study of whether NEW Tx will be feasible with regards to recruitment, retention, blinded assessments, and therapist adherence to NEW Tx⁴³. *Hypothesis 1b:* Participants will report high satisfaction with the treatment (CSQ-8) and acceptability (NEW Tx Scale) over the study duration (i.e., 20-weeks) in a nonrandomized trial ($n = 6$).
- ii. **Aim 2:** Feasibility and Acceptance of NEW Tx and its Evaluation in the Randomized Pilot Trial ($n = 40$). *Hypothesis 2a:* A pilot study of whether NEW Tx will be feasible with regards to recruitment, randomization, retention, blinded assessments, and therapist adherence to NEW Tx⁴³. *Hypothesis 2b:* Participants will report high expectations for the treatment (CEQ) and high satisfaction and acceptability with the treatment (CSQ-8; Post-Tx Questionnaire; NEW Tx Scale) in a 20-week nonrandomized trial ($n = 6$).

B. Exploratory Aims

- i. **Aim 3a:** Reducing Medical Burden in the Randomized Pilot Trial. Pilot test ($n = 40$) the efficacy of NEW Tx in improving medical burden using the Framingham Risk Score (FRS). *Hypothesis 3a:* Over the course of 20-weeks (18 sessions) the NEW Tx group will have a lower FRS compared to treatment as usual (TAU) in the randomized pilot trial.
- ii. **Aim 3b:** Symptoms and Functioning in the Randomized Pilot Trial. Examine the efficacy of NEW Tx in improving functioning and symptoms of BD. *Hypothesis 3b:* Over the course of 20-weeks (18 sessions) the NEW Tx group will improved functioning (LIFE-RIFT) and symptoms (YMRS, MADRS) compared to TAU in the randomized pilot trial.
- iii. **Aim 3c:** Moderator and Mediator of NEW Tx in the Randomized Pilot Trial. Investigate a potential moderator and mediator of treatment response. *Hypothesis 3c.1:* Individuals with higher baseline BMI (>30) will moderate the between treatment effect size for medical burden (FRS) in the randomized pilot trial, such that of NEW Tx will have lower FRSs. *Hypothesis 3c.2:* Mastery of the diet (food diaries) and exercise (exercise duration from Exercise Questionnaire) modules of NEW Tx will mediate the association of NEW Tx and improvement in medical burden (FRS).

III. INTERVENTION MODULES AND OVERVIEW

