This module is integrated throughout the first two modules as it reinforces the importance of making healthy decisions (e.g., food choices, exercise, increasing behavioral activation) and helps to problem solve obstacles to making these choices. This module is reflected in the use of CBT-based strategies that focus on increasing adherence to the nutrition and exercise modules as well as other healthy choices (e.g., reduction of caffeine, smoking, substance use). For example, we discuss that having 5 to 6 smaller meals throughout the day is an ideal meal plan as it is healthier and enhances their routine and energy level, opposed to using caffeine or smoking as stimulants. We focus on these other lifestyle choices as exercise reduces the craving for smoking⁵¹ and substance use⁵² as well as seems to buffer against substance abuse⁵³.

Similarly, we encourage participants to choose a feasible time every other day to exercise and to use positive rewards when meeting exercise and diet goals. In this module, we also discuss important aspects of behavioral activation, such as balancing mastery and pleasurable tasks and setting appropriate mood-dependent schedules. An important aspect of enhancing healthy lifestyle choices is accounting for mood-specific shifts in their activation. For example, during (hypo)manic episodes bipolar individuals tend to be impulsive and overly energetic, and thus their lifestyles often become chaotic and erratic. In contrast, during depressive episodes, bipolar individuals lose this behavioral activation and thus, tend to isolate or withdraw. In this module, we stress the importance of having two feasible choices or plans: one for elevated moods and one for depressed moods. Both plans emphasize structure and healthy coping behaviors, but the activities vary. We also use reward charts to reinforce healthy decisions and challenge self-defeating thoughts (e.g., “I can’t change”). This module also incorporates motivational interviewing techniques which are effective in helping individuals gain insight into their unhealthy behaviors and the need for change⁵⁴.

IV. RESEARCH DESIGN AND METHODS

A. Overview

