An EKG will be required for participants over the age of 40, if clinically indicated, to further minimize potential risks associated with exercising. For clinical monitoring and assessment of adverse events, a fasting blood draw will be conducted at Week 0, Week 10, and Week 20. For the waitlist group (i.e., TAU participants who choose to receive NEW Tx after 20 weeks), fasting blood draws will be conducted at Weeks 30, Week 40, and Week 52, in addition to the aforementioned draws. Drug screens will not be required; however, administration of drug screening as part of ongoing treatment is at the discretion of the treating physician at any time after consultation with the participant.

C. Diagnostic and Clinical Assessments

- i. **Extended Mini-International Neuropsychiatric Interview** (MINI⁵⁷) will be used to establish DSM-IV diagnoses including BD, substance use, and eating disorders.
- ii. **Demographics, Medical History, and Psychiatric History** forms will assess any pertinent medical or psychiatric conditions that may impact the participants' eligibility or treatment in this study.
- iii. **Montgomery Asberg Depression Rating Scale** (MADRS⁵⁸) is a 10-item clinician-rated measure of depression that assesses the presence and severity of patient's current depressive symptoms.
- iv. **Young Mania Rating Scale** (YMRS⁵⁹) is an 11-item, clinician-rated measure that assesses the presence and severity of patient's current symptoms of mania.
- v. **Clinical Global Impression-Bipolar Illness** (CGI-BP⁶⁰) is a one item illness severity score that is a widely accepted, reliable, and valid assessment of global illness in BD⁶¹. The CGI-BP is a modified version of the CGI designed specifically for use in assessing global illness severity in patients with BD. This version assigns ratings for mania, depression, overall severity, and side effects.
- vi. **Clinical Monitoring Form** (CMF) Medication Module⁶² will track medication and dosage changes and whether the subject is taking medications for blood pressure (used to calculate the FSR score).
- vii. **Food Diaries** or a self-report record of foods and calories consumed will be completed by participants between study visits as needed. Selected food diaries will be reviewed by a dietitian (as needed).

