- viii. **Exercise Questionnaire** (EQ) is a modified version of the Exercise History and Attitude Questionnaire which has been used in a wide variety of settings^{63, 64}. It is typically administered to healthy populations; thus, some items were excluded that were not likely to pertain to BD. This questionnaire assesses baseline (i.e., past) exercise history as well as ongoing exercise duration and frequency at follow-up study visits⁶⁵.
- ix. **LIFE- Range of Impaired Functioning Tool** (LIFE-RIFT^{66, 67}) assesses the extent to which medical burden has impacted current functioning.
- x. **Framingham Risk Score** (FRS) will be used to estimate medical burden as it is designed to estimate risk in adults (age > 20) to predict 10-year risk for myocardial infarction and coronary death. The FRS is calculated

based on six indices: age, gender, total cholesterol, HDL cholesterol, smoker (Y/N), systolic blood pressure, and medications to treat high blood pressure (Y/N). It is one of the most widely validated and cited clinical prediction scores, and although several modifications have been proposed, a recent review of over 1900 studies found that these studies had “flaws in their design, analyses, and reporting that cast some doubt on the reliability of the claims for improved prediction”⁶⁸. The Medical History form will collect the patient data necessary to calculate the FRS score.

- xi. **Physical Activity Readiness Questionnaire (PAR-Q⁶⁹)** is a seven-item, self-report questionnaire to screen individuals for starting an exercise program. In addition to the PAR-Q, an EKG will be required for participants over the age of 40, if clinically indicated, to further minimize potential risks associated with exercising.
- xii. **Credibility/Expectancy Questionnaire (CEQ⁷⁰)** is a 6-item, self-report questionnaire to assess patients' perceptions of and expectations for treatment before the study begins.
- xiii. **Client Satisfaction Questionnaire-8 (CSQ-8⁷¹)** is a reliable and valid self-report of participants' acceptability of treatment. This is an assessment of client/patient satisfaction with their care and perceived quality and tolerability of NEW Tx.
- xiv. **NEW Tx Scale** is a 10-item scale to assess participants' acceptability of NEW Tx. This scale also includes a comments section to solicit unstructured feedback from participants on NEW Tx.

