ET= Early Termination. Vitals = Height (at Week 0 and Week 20), weight, waist circumference, blood pressure, pulse, and Dual X-Ray Absorptiometry (i.e., body composition). ** Includes lipid profile (i.e., cholesterol, triglycerides), metabolic panel (i.e., blood urea nitrogen (BUN), creatinine (Cr), electrolytes, blood glucose level), complete blood count (CBC), and thyroid stimulating hormone (TSH). C reactive protein (CRP) and inflammatory marker panels (Human TH1/TH2 10-Plex (IFN-g, IL-1b, IL-2, IL-4, IL-5, IL-8, IL-10, IL-12p70, IL-13, TNF-a)) will be included at pre- and post-treatment visits. A urine pregnancy test will be administered at Week 0 to determine eligibility. An EKG will be completed at Week 0 for participants \geq 40-years-old, if clinically indicated.

¹As needed.

†For the TAU group, will only be collected at Weeks 0, 10, and 20

Table 2. Schedule of Assessments for the Waitlist Group (TAU participants who choose to receive NEW Tx)Weeks	21	22	23	24	25	26	27	28	29	30	31	32	33	34	35	36	37	38	39	40	52
										Mid-tx									Post-tx	Follo w-up	
CGI-BP										x									x	x	
Blood Draw**										x									x	x	
Vitals										x									x		
DXA scan																			x		
CMF										x									x	x	
MADRS										x									x	x	
YMRS										x									x	x	
LIFE-RIFT										x									x	x	
NEW Tx Scale																			x	x	
CSQ-8																			x	x	
URICA	x																		x	x	
Met Cart	x																		x		
Post-Tx Questionnaire																			x	x	
EQ	x	x	x	x	x	x	x	x	x	x	x	x	x	x	x	x	x	x	x	x	
Intent-to-Attend	x	x	x	x	x	x	x	x	x	x	x	x	x	x	x	x	x	x	x	x	
Food Diaries	x ¹																				

ET= Early Termination. Vitals = weight, waist circumference, blood pressure, pulse, and Dual X-Ray Absorptiometry (i.e., body composition). ** Includes lipid profile (i.e., cholesterol, triglycerides), metabolic panel (i.e., blood urea nitrogen (BUN), creatinine (Cr), electrolytes, blood glucose level), complete blood count (CBC), and thyroid stimulating hormone (TSH). C reactive protein (CRP) and inflammatory marker panels (Human TH1/TH2 10-Plex (IFN-g, IL-1b, IL-2, IL-4, IL-5, IL-8, IL-10, IL-12p70, IL-13, TNF-a)) will be included at pre- and post-treatment visits. A urine pregnancy test will be administered at Week 0 to determine eligibility.

¹As needed.

D. Independent Evaluator Training

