- iii. **Aim 3: Exploratory Aims (Phase II).** *Hypotheses 3a and 3b:* Between treatment group effects sizes (and 95% CI) will be calculated. To supplement this, Mann-Whitney tests will compare treatment groups on medical burden (as measured by FRS) (*Hypothesis 3a*) and on improvement in symptoms (MADRS, YMRS) and functioning (LIFE-RIFT) (*Hypothesis 3b*) based on change from baseline. *Hypothesis 3c.1:* We will investigate baseline BMI as a potential moderator of treatment response. The focus will be on the magnitude of the effect, not on significance testing. The between treatment group effect sizes (i.e., FRS, MADRS, YMRS, LIFE-RIFT) will be compared with those who have high baseline BMI (> 30) versus low BMI (< 30). *Hypothesis 3c.2:* Mastery of the diet (Nutrition Data System score of food diaries) and exercise (weekly exercise duration from Exercise Questionnaire) modules will mediate the association of NEW Tx and improvement in medical burden (FRS). The

dependent variable will represent change in the FRS score from time of completion of respective module. The mediators will be tested separately. Differential between treatment group effect sizes for those who did and did not master the modules will provide evidence of a mediator of treatment.

C. Rate of Attrition

Some attrition (i.e., 20%) is expected and this can result in bias and reduce power, precision and generalizability⁷⁹. Consistent with the Intent to Treat principle⁸⁰, we will continue with the assessments for the study duration, even among those who fail to comply with the treatment⁸¹. As one aspect of the feasibility study, we will assess the likelihood to attrite using the “Intent to Attend” measure⁷².

D. Power Analysis

The sample sizes for the Phase I and II trials are based primarily on the fundamental aim of this project: feasibility. The N is not based on what is needed for inferential analyses as they are not a fundamental aspect of the design. Power analyses are not indicated for the proposed exploratory analyses. We acknowledge that we will not have sufficient power to detect large effects (e.g., $d = .80$).

IX. REFERENCES

1. Hennekens C. Increasing global burden of cardiovascular disease in general populations and patients with schizophrenia. *Journal of Clinical Psychiatry*. 2007;68(suppl 4):4-7.

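### Smoking status is an input to the Framingham Risk Score but is scheduled only at Week 0, so change in the score cannot register quitting or starting

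*Combined protocol and SAP*

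**What the plan says.** Section IV.C.x gives the inputs to the FRS as age, gender, total and HDL cholesterol, smoker (Y/N), systolic blood pressure and blood-pressure medication (Y/N). On their source it says: "The Medical History form will collect the patient data necessary to calculate the FRS score". Table 1 marks Medical Hx once, at Week 0. Table 2, the "Schedule of Assessments for the Waitlist Group", has no Medical History row.

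For one other yes/no input the plan does name a repeated source. Section IV.C.vi says the Clinical Monitoring Form (CMF) records "whether the subject is taking medications for blood pressure (used to calculate the FSR score".

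Smoking is part of the trial's rationale and of its treatment. Section I says that people with bipolar disorder "use maladaptive coping strategies for stress, such as smoking, that increase their medical burden". Section III.C lists among the Wellness module's aims "other healthy choices (e.g., reduction of caffeine, smoking, substance use".

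Aim 3a (Section II.B) is to test "the efficacy of NEW Tx in improving medical burden using the Framingham Risk Score (FRS". Under Section VIII.B.iii, "Mann-Whitney tests will compare treatment groups on medical burden (as measured by FRS", with the comparison "based on change from baseline". For Hypothesis 3c.2 the same section instead measures FRS change from completion of the relevant module.

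**The concern.** A change score can reflect only inputs that are measured again. If smoking status is known only at Week 0, the only value available for the Week 10 and Week 20 scores is the Week 0 answer. A participant who quits or starts then has a wrong later score, and the change in FRS omits a behaviour that the intervention sets out to alter.

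FRS is the medical-burden outcome for Hypotheses 3a, 3c.1 and 3c.2, and Section IV.A gives estimating an effect size as one purpose of Phase II. If NEW Tx produced more net quitting than TAU, that part of its effect would be missing from the estimate.

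Repairing this informally during the trial could make matters worse. Therapists would hear about smoking in NEW Tx sessions, but TAU participants have no such sessions in Weeks 0 to 20. Status updated from that contact would be unblinded and would differ by arm.

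**Working it through.** **Step 1: trace each FRS input to its source and schedule.**

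| FRS input | Source in the plan | Collected after baseline in Weeks 0 to 20? |
|---|---|---|
| Age, gender | Baseline forms | Not needed; treatment cannot change them |
| Total and HDL cholesterol | Fasting blood draw (IV.B, Table 1) | Yes, Weeks 10 and 20 |
| Systolic pressure | Vitals (Table 1) | Yes, mid- and post-treatment |
| Blood-pressure medication | CMF (IV.C.vi, Table 1) | Yes, mid- and post-treatment |
| Smoker (Y/N) | Medical History form (IV.C.x, Table 1) | No, Week 0 only |

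None of the other instruments fills the gap. The MINI covers substance use diagnoses but is given at Week 0 only. The blood panel listed under Table 1 includes no nicotine marker. The CGI-BP, MADRS, YMRS, LIFE-RIFT, URICA, Exercise Questionnaire, Intent to Attend, food diaries and satisfaction scales are not described as recording smoking.

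**Step 2: the consequence for the change score.** With a single value per person, the smoking term is the same at both ends of the interval, so its contribution to change is zero for everyone. This also holds for 3c.2. On-treatment blood draws fall only at Weeks 0, 10 and 20, so those are the only on-treatment visits at which FRS can be computed from current lipids.

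**Step 3: how many scores could be wrong.** The plan has no figure to reproduce. The following is an illustration.

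- From the documents: Phase II n = 40 (Section II) or n = 60 (Sections IV.A and IV.B), allocated 1:1, giving 20 or 30 per arm. With 20% attrition (VIII.C), 20 × 0.8 = 16 or 30 × 0.8 = 24 complete.
- Assumed, not from the documents: smoking prevalence p = 30% to 50%; quit rate among NEW Tx smokers q = 10% to 20%. Then p × q runs from 0.30 × 0.10 = 0.03 to 0.50 × 0.20 = 0.10.

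Expected wrong Week 20 scores in NEW Tx = n × p × q:

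| NEW Tx arm | Low (0.03) | High (0.10) |
|---|---|---|
| 20 randomised | 0.6 | 2.0 |
| 30 randomised | 0.9 | 3.0 |
| 16 completers | 0.48 | 1.6 |
| 24 completers | 0.72 | 2.4 |

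The chance of at least one such completer is 1 − (1 − pq)^n. It runs from 1 − 0.97^16 = 0.386 to 1 − 0.90^24 = 0.920.

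With wider assumptions (p = 20% to 50%, q = 5% to 20%, so pq = 0.01 to 0.10), 16 completers give 0.16 to 1.6 wrong scores and a chance of 0.15 to 0.82. For 24 completers the figures are 0.24 to 2.4 and 0.21 to 0.92. People who start smoking are not counted.

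**Step 4: effect on the mean between-arm difference.** Let W be the average FRS weight of smoking, which the documents do not give. Understatement = p × (q in NEW Tx − q in TAU) × W.

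- TAU quit rate 0%: 0.03W to 0.10W.
- TAU quit rate 5%: 0.30 × (0.10 − 0.05) = 0.015W to 0.50 × (0.20 − 0.05) = 0.075W.
- Equal quit rates: zero, although individual scores are still wrong.

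**The case against.** The strongest reply is that the evidence is silence. The forms are not reproduced, and the plan does not treat the Medical History form as the sole source of FRS inputs, since it assigns blood-pressure medication to the CMF. A repeated form might already ask about smoking. Nor does the plan say that the Week 0 answer is carried forward. Both points are fair as limits: carry-forward is an inference from the named source and its schedule. They do not close the gap, because someone following the documents would have no smoking status to enter at Week 10 or Week 20.

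A second reply concerns size. Smoking is one example within a module, it is framed as reduction, and modules are chosen to suit the individual. Few may quit, and cutting down does not move a yes/no input. The percentages follow from unsourced assumptions, W is unknown, and a mean shift does not carry over directly to a rank-based Mann-Whitney test. All of this stands, and it is why the figures show only what is plausible. Equal net quitting would leave the between-arm mean difference unaffected.

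Third, the aim is exploratory and the plan itself disclaims adequate power, so no primary conclusion is at risk. That is correct and limits the priority of the point. The waitlist schedule also matters only if FRS is computed there, and the plan describes no such analysis.

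Finally, status might be recovered by recall at Week 32. That is possible, but recall months later is a poorer source than a question asked at the visit.

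**Conclusion.** The concern holds. As scheduled, smoking status is collected once, and it is the only FRS input open to change by treatment without a described repeat source. Change in FRS therefore cannot reflect quitting or starting.

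Under the main assumptions, roughly half a participant to two and a half participants among the NEW Tx completers would be misclassified; the wider assumptions lower the bottom of that range. The bias in the between-arm difference is downward if NEW Tx produces more net quitting and zero if quitting is equal. Its size in FRS units cannot be stated without W.

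The conclusion rests on the plan's silence about any repeated smoking question, and one sentence from the sponsor could resolve it. The consequence is confined to Hypotheses 3a, 3c.1 and 3c.2. The feasibility and acceptability aims are unaffected. It should be corrected because the remedy is so cheap, not because the trial depends on it.

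**What to change.** If an existing form already re-asks smoking, name that form and its visits in Section IV.C.x and Table 1. Otherwise, add one current-smoker (Y/N) item, asked by the blinded independent evaluator in both arms at Weeks 0, 10 and 20, and state that each FRS uses the smoking status from the same visit. Those visits also serve Hypothesis 3c.2. Extend the item to Week 32 and the waitlist visits only if FRS is to be computed there.

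The cost is one question and one REDCap field at visits already scheduled, with no new procedure. The drawback is that the answer is unverified self-report, and NEW Tx participants, who know their arm, may over-report quitting. Reporting FRS change both with updated smoking status and with status held at baseline would show how much of any difference depends on those answers.

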- ii. **Phase II:** In this phase, we will pilot test the NEW Tx methods compared to TAU ($n = 60$) to further examine feasibility, to estimate an effect size, and to explore its efficacy for reducing medical burden. TAU will be the control group in the Phase II pilot study as it is the standard treatment in the Massachusetts General Hospital (MGH) Bipolar Clinic and Research Program. Participants randomized to TAU who complete the first 20 weeks of the study will have the option to receive NEW Tx. TAU participants who chose to receive NEW Tx (the waitlist group) will follow the same procedures as the NEW Tx group over an additional 20 weeks such that they will have assessments at Weeks 30, (mid-treatment), 40 (post-treatment), and 52 (follow-up) (see Table 2). For TAU, medication and dosage changes are allowed as long as the change is recommended based on the guidelines and participants remain on a mood stabilizer. Medication changes will be monitored with the Clinical Monitoring Form Medication Module. All participants will have a three-month follow-up visit during which post-treatment measures and assessments will be repeated. Participants will be recruited with the same criteria as the nonrandomized trial, but will be randomized using a 1:1 allocation ratio with a blocking strategy. The assessments will be similar to those used in Phase I. In addition to the study staff utilized in Phase I, clinicians with training in CBT and mood disorders will be added as NEW Tx therapists.

B. Participant Selection and Recruitment

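### Table 2 schedules blood and the CMF but no Vitals at the waitlist group's Week 52 follow-up, so blood pressure and weight are not collected and the exploratory FRS cannot be derived there

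*Combined protocol and SAP*

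**What the plan says.** Section IV.C, item x, builds the FRS from "age, gender, total cholesterol, HDL cholesterol, smoker (Y/N), systolic blood pressure, and medications to treat high blood pressure (Y/N"). Three of these have a scheduled source that can be followed over time:

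- Lipids come from the blood draw.
- Systolic pressure comes from Vitals, which the Table 2 footnote defines as "Vitals = weight, waist circumference, blood pressure, pulse" and body composition.
- Treatment for hypertension comes from the CMF, which records "whether the subject is taking medications for blood pressure".

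Item x adds: "The Medical History form will collect the patient data necessary to calculate the FRS score". That form is marked at Week 0 only in Table 1 and has no row in Table 2.

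On follow-up, section IV.A (Phase II) states: "All participants will have a three-month follow-up visit during which post-treatment measures and assessments will be repeated". The same paragraph puts crossed-over TAU participants on the NEW Tx arm's procedures, with assessments at Weeks 30, 40 and 52.

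On blood, section IV.B says that, for clinical monitoring and adverse events, "a fasting blood draw will be conducted at Week 0, Week 10, and Week 20". It then adds Weeks 30, 40 and 52 for the waitlist group. Week 32 is not mentioned.

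**The concern.** The schedule tables are what site staff work from. Table 2 brings the waitlist participant in at Week 52, draws blood and completes the CMF, but asks for no blood pressure or weight. Systolic pressure is an FRS component and weight is a direct target of the intervention. A reading not taken at that visit cannot be recovered later.

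The NEW Tx arm has Vitals at its own three-month follow-up in Table 1, so the two groups are treated differently at the same point after treatment, although the text says their procedures are the same. What is at stake is the description of how medical burden and weight behave three months after NEW Tx in the crossed-over participants.

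A smaller issue sits beside it. Table 1 shows a Week 32 blood draw that section IV.B does not list, so a site working from the text alone could miss those lipids.

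**Working it through.** No statistical formula applies. The check sets the tables and text side by side.

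**1. Marks per row.** In the text copy of the tables, some rows sit one column to the left of their week headers. I therefore read them by number of marks and by the Pre/Mid/Post/Follow-up labels.

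| Row | Table 1 (NEW Tx and TAU) | Table 2 (waitlist) |
|---|---|---|
| Blood Draw | 4: pre, mid, post, follow-up | 3: mid, post, follow-up |
| CMF | 4: pre, mid, post, follow-up | 3: mid, post, follow-up |
| Vitals | 4: pre, mid, post, follow-up | 2: mid, post |

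Section IV.B confirms the reading of Table 2, since its waitlist draws at Weeks 30, 40 and 52 match the three Blood Draw marks. The Vitals row keeps an empty cell in the follow-up position. A count is not affected by a column shift, but it would not reveal a mark lost in conversion.

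**2. Measured FRS inputs by visit.**

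| Visit | Lipids | Blood pressure | Hypertension medication |
|---|---|---|---|
| Weeks 0, 10, 20 | yes | yes | yes |
| Week 32, if Table 1 governs | yes | yes | yes |
| Week 32, if the IV.B list were exhaustive | not listed | yes | yes |
| Weeks 30, 40 | yes | yes | yes |
| Week 52 (Table 2) | yes | **no** | yes |

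The only visit with a draw but no blood pressure is Week 52. At Week 32 nothing is missing from the table; the text and the table disagree.

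**3. Smoking status.** Age and gender need no repeat measurement, but smoking can change. The Medical History form is the named source of FRS data and is marked at Week 0 only. No later source for smoking is named, so adding Vitals at Week 52 would not by itself complete the FRS there.

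**4. Number affected.** The document gives the Phase II size as 40 (section II) and as 60 (sections IV.A and IV.B). With 1:1 allocation:

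- 40 / 2 = 20 TAU participants, or 60 / 2 = 30.
- If the 20% attrition in section VIII.C applied equally to TAU by Week 20: 20 × 0.8 = 16, or 30 × 0.8 = 24.
- Crossover is optional and its uptake is not stated, so the number reaching Week 52 lies between 0 and those figures. The 20 or 30 is a ceiling.

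Within that group, Week 52 blood pressure, weight and FRS are scheduled for none.

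**The case against.** The strongest reply is that nothing the plan commits to analyse depends on this cell. The FRS belongs to an exploratory aim. Hypothesis 3a covers 20 weeks, section VIII.B specifies change from baseline with no follow-up FRS analysis, and Weeks 0 and 20 have both blood and Vitals. The waitlist group at Week 52 has no concurrent control. The follow-up sentence in IV.A cannot be literal for every measure, because neither table marks DXA or the metabolic cart at follow-up. The Week 52 draw also has a stated safety purpose, so it is not wasted without an FRS.

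All of this stands, and it rules out three stronger readings that a reader might infer:

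- *The FRS cannot be computed at follow-up in either group.* Table 1 schedules blood, Vitals and CMF at Week 32. Section IV.B is a safety-monitoring sentence that leaves out one draw. It does not say that its list is complete, and silence should not override an explicit table entry.
- *The protocol promises a follow-up FRS.* No passage names one. It can only be inferred from the general follow-up sentence.
- *Durability of the main efficacy result is lost.* The primary aims are feasibility and acceptance, and the randomized comparison does not use Week 52.

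The reply does not explain why Vitals is repeated at follow-up for the NEW Tx arm but not for a group that is meant to follow the same procedures.

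**Conclusion.** The point holds for Week 52 and is minor. Table 2 omits Vitals at the waitlist follow-up, in conflict with section IV.A and out of line with Table 1. If the table is followed, blood pressure and weight are not collected there and the exploratory FRS cannot be derived for any of at most 20 (n = 40) or 30 (n = 60) participants. The Vitals gap leaves the randomized 20-week comparison unaffected.

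The Week 32 item is a text/table mismatch to reconcile, not a missing input. The smoking gap is one of documentation: no post-baseline source is named, which does not show that smoking will go unrecorded.

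The conclusion assumes that the empty Vitals cell in Table 2 is also empty in the source PDF, and that blood pressure has no scheduled source in Table 2 other than Vitals.

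**What to change.** 1. Check the Week 52 Vitals cell of Table 2 against the source PDF.
2. If it is empty, mark Vitals at Week 52 so that Table 2 agrees with section IV.A and Table 1. Specify blood pressure and weight: the footnote's definition of Vitals also includes DXA, which has its own row with no follow-up mark, so the new mark should not imply another scan.
3. Reconcile the section IV.B list of blood draws with Table 1 on Week 32.
4. State at which visits the FRS is derived, and record smoking status at each of them on a named form.

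The cost is schedule wording, one added smoking item, and a few minutes at a visit that already includes a blood draw. Sample size and the planned analyses do not change.
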